9.4 Statistical Analyses

9.4.1 General Considerations

All individual data will be listed as measured. All statistical summaries and analyses will be performed using SAS software (SAS Institute Inc, Cary, North Carolina, USA).

Continuous data will be summarized using an 8-point descriptive summary (n, mean, SD, median, IQR [25% quartile, 75% quartile], minimum, and maximum) or 7-point descriptive summary (n, mean, SD, CV, median, minimum, and maximum) unless otherwise specified.

Categorical data will be summarized using the frequency of events and percentage of total events.

Baseline definitions for each endpoint will be defined in the SAP.

Data will be presented by treatment group. Changes in primary, secondary, and exploratory endpoints will be analyzed over time, with change from baseline summarized for each post-baseline time point measured.

All efficacy analyses will be conducted on the ITT Population using a 2-sided alpha of 0.05. The primary endpoint and secondary endpoints will be reported using a multiplicity algorithm.

Efficacy analyses at Week 18 (primary and secondary) will compare tildacerfont treatment groups to placebo. Efficacy analyses at Week 76 will evaluate change from baseline only.

For missing data, a retrieved dropout approach will be used in which missing endpoint data for subjects who discontinued early will be imputed using data collected from subjects after discontinuation of study drug.

Any changes to the protocol-specified analyses will be pre-specified in the SAP prior to database lock.

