### 13.3.2 Dose Response Statistical Hypothesis

For the Primary Efficacy Analysis, the null hypothesis is that there is no difference in the profile of log A4 change from baseline through 12 weeks of blinded randomized treatment between tildacerfont and placebo. The alternative hypothesis is that there is difference in the profile of log A4 change from baseline through 12 weeks of blinded randomized treatment between tildacerfont and placebo.

To assess this dose response hypothesis, repeated measures random coefficients mixed-effects model will be used:

$$y_{ijt} = (\beta_0 + \xi_i) + (\beta_1 + \eta_i)t + (\beta_2 + \theta_i)t^2 + \beta_{4j}I_j + \beta_{5j}I_jt + \beta_{6j}I_jt^2 + \beta_7\kappa + \beta_8G + \beta_9D + e_{ijt}$$

where:

$y_{ijt}$  is the log A4 change from baseline value for subject  $i$ ,  $i = 1, \dots, N$ , at time  $t$  in treatment group  $j$ ,  $j = 1, 2, 3, 4$  (1 = 200mg tildacerfont, 2 = 100mg tildacerfont, 3 = 50mg tildacerfont and 4 = placebo),  $I_t$  is the indicator for randomised treatment ( $I_t = 1$  for tildacerfont 200mg,  $=2$  for 100mg,  $=3$  for 50mg and  $=4$  for placebo),  $\kappa$  is log baseline A4 value,  $G$  is the indicator for sex ( $G = 1$  male,  $G = 0$  female) and  $D$  baseline GC dose (in HCe),

$\beta_0$  is the fixed intercept effect.

$\beta_1$  is the fixed effect of the linear component of time

$\beta_2$  is the fixed effect of the quadratic component of time

$\beta_{4j}$  is the fixed effect of treatment  $j$  parametrized such with  $\beta_{44} = 0$

$\beta_{5j}$  is the effect of treatment  $j$  on the linear component of time parametrized such that  $\beta_{54} = 0$

$\beta_{6j}$  is the effect of treatment  $j$  on the quadratic component of time parametrized such that  $\beta_{64} = 0$

$\beta_7$  is the fixed effect of baseline log A4

$\beta_8$  is the fixed effect of gender

$\beta_9$  is the fixed effect of baseline GC dose

$\xi_i$  is the random effect of subject  $i$  on the intercept

$\eta_i$  is the random effect of subject  $i$  on the linear component of time

$\theta_i$  is the random effect of subject  $i$  on the quadratic component of time

$e_{ijt}$  is the random error for subject  $i$  on treatment  $j$  and time  $t$ .

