### 13.3.3 Dose Response Modeling and Testing

Statistical testing for dose response will be performed using the repeated measures random coefficients mixed-effects model described in [Section 13.3.2](#). A4 values will be log transformed prior to analysis. The model will comprise of the log A4 change from baseline through to study Week 18, i.e. though 12 weeks of double blind randomized treatment; note the actual time, in days, from baseline to each post baseline A4 value through to study week 18 will be used in this analysis. Randomized treatment group and sex will be included in the model as class factors and baseline GC dose (in HCe) as continuous covariate. Subject specific intercept, time (in days)

and time x time random effects will be included. Further, randomized treatment by time and randomized treatment by time x time interactions will be included. The model will be fitted using maximum likelihood estimation. If the variance component for time or time x time are estimated to be zero then the corresponding term (or terms) will be retained in the model as fixed effects and the analysis re-run.

To test the union intersection hypothesis  $H_{0L} \cap H_{QL}$ , the model will be fitted with and without the randomized treatment by time and randomized treatment by time squared interactions terms. The difference in -2 log likelihood between models will be compared to the  $\chi^2_{df}$  cumulative distribution function on the appropriate degrees of freedom (i.e.  $df = 6$ ), this will provide the p-value to determine if the union intersection hypothesis can be rejected at the 10% alpha level; if so then there is evidence for a treatment effect of tildercerfont over placebo.

The fitted A4 change from baseline versus time profile will be extracted from the model for each randomized treatment and displayed graphically, superimposed upon the A4 time profiles for individual subjects.

Note, the programming of the repeated measures random coefficients mixed-effects model is particularly complex, hence example SAS codes perform the analysis are presented in Appendix D.

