LBASE=LOG (BASE) ;
LCFB=LPULSE-LBASE;
RUN;
DATA STUDY2;
  SET STUDY2;
  G=EXERTYPE;
RUN;

PROC SORT DATA=STUDY2;
  BY ID TIME;
RUN;

** FULL MODEL WITH TIME*G AND TIME*TIME*G = DOSE RESPONSE PARAMETERS **;

PROC MIXED DATA=STUDY2 COVTEST NOCLPRINT METHOD=ML ;
  CLASS ID G ;
  MODEL PULSE = BASE TIME G TIME*G TIME*TIME TIME*TIME*G /
  SOLUTION OUTP=PRED1RX OUTPM = PRED1FX;
  RANDOM INTERCEPT TIME TIME*TIME / SUBJECT = ID SOLUTION;

  ** ESTIMATES WHEN BASELINE = 90 BPM, I.E. LOG BASE = 4.5 **;
ESTIMATE "INTERCEPT: 1 " INTERCEPT 1 BASE 90 G 1 0 0 ;
ESTIMATE "INTERCEPT: 2 " INTERCEPT 1 BASE 90 G 0 1 0 ;
ESTIMATE "INTERCEPT: 3 " INTERCEPT 1 BASE 90 G 0 0 1 ;

  ** TRT EFFECTS AND CONTRASTSAT 600 DAYS **;

ESTIMATE "VALUE AT 600 1" INTERCEPT 1 BASE 90 G 1 0 0 TIME 600 G*TIME 600 0 0
TIME*TIME 360000 G*TIME*TIME 360000 0 0 ;
ESTIMATE "VALUE AT 600 2" INTERCEPT 1 BASE 90 G 0 1 0 TIME 600 G*TIME 0 600 0
TIME*TIME 360000 G*TIME*TIME 0 360000 0 ;
ESTIMATE "VALUE AT 600 3" INTERCEPT 1 BASE 90 G 0 0 1 TIME 600 G*TIME 0 0 600
TIME*TIME 360000 G*TIME*TIME 0 0 0 ;
ESTIMATE "VALUE AT 600 1-3" G 1 0 -1 TIME 0 G*TIME 600 0 -600 TIME*TIME 0 G*TIME*TIME 360000 0 0;
ESTIMATE "VALUE AT 600 2-3" G 0 1 -1 TIME 0 G*TIME 0 600 -600 TIME*TIME 0 G*TIME*TIME 0 360000 0 ;
ESTIMATE "LINEAR CONTRAST @ 600" G -1 0 1 TIME 0 G*TIME -600 0 600
TIME*TIME 0 G*TIME*TIME -360000 0 0;
ESTIMATE "QUADRATIC CONTRAST @ 600" G 1 -2 1 TIME 0 G*TIME 600 -1200 600
TIME*TIME 0 G*TIME*TIME 360000 -720000 0;
ODS OUTPUT FITSTATISTICS=FIT1;
ODS OUTPUT SOLUTIONF=F1;
ODS OUTPUT COVPARMS =C1;

TITLE 'RC MODEL TIME G TIME*G TIME*TIME TIME*TIME*G';
RUN;
TITLE;

** REDUCED MODEL WITH TIME*G AND TIME*TIME*G = DOSE RESPONSE PARAMETERS **;
PROC MIXED DATA=STUDY2 COVTEST NOCLPRINT METHOD=ML ;
  CLASS ID G ;
  MODEL PULSE = BASE TIME G TIME*TIME /
  SOLUTION;
  RANDOM INTERCEPT TIME TIME*TIME / SUBJECT = ID SOLUTION;

  ** ESTIMATES WHEN BASELINE = 90 BPM, I.E. LOG BASE = 4.5 **;
ESTIMATE "INTERCEPT: 1 " INTERCEPT 1 BASE 90 G 1 0 0 ;
ESTIMATE "INTERCEPT: 2 " INTERCEPT 1 BASE 90 G 0 1 0 ;
ESTIMATE "INTERCEPT: 3 " INTERCEPT 1 BASE 90 G 0 0 1 ;

  ** TRT EFFECTS AND CONTRASTSAT 600 DAYS **;
```

```
ESTIMATE "VALUE AT 600 1" INTERCEPT 1 BASE 90   G   1 0 0   TIME  600 TIME*TIME  360000  ;
ESTIMATE "VALUE AT 600 2" INTERCEPT 1 BASE 90   G   0 1 0   TIME  600 TIME*TIME  360000  ;
ESTIMATE "VALUE AT 600 3" INTERCEPT 1 BASE 90   G   0 0 1   TIME  600 TIME*TIME  360000  ;

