ESTIMATE "VALUE AT 600 1-3" G   1 0 -1 TIME   0   TIME*TIME  0   ;
ESTIMATE "VALUE AT 600 2-3" G   0 1 -1 TIME   0   TIME*TIME  0   ;
ESTIMATE "LINEAR CONTRAST @ 600"      G   -1 0 1 TIME   0   TIME*TIME  0   ;
ESTIMATE "QUADRATIC CONTRAST @ 600"    G   1 -2 1 TIME   0   TIME*TIME  0   ;

ODS OUTPUT FITSTATISTICS=FIT2;
ODS OUTPUT SOLUTIONF=F2;
ODS OUTPUT COVPARMS =C2;

TITLE 'RC MODEL TIME G TIME*TIME';
RUN;
TITLE;

DATA C1;
  SET C1;
  TP='COVPARM';
RUN;
DATA F1;
  SET F1;
  TP='FIXED  ';
RUN;

DATA DF1;
  LENGTH P $24;
  LENGTH MODEL $12;
  SET F1(RENAM=(EFFECT=P) ) C1(RENAM=(COVPARM=P));
  IF ESTIMATE NE 0;
  DUM=1;
  MODEL='FULL';
  KEEP MODEL TP ESTIMATE STDERR P DUM;
RUN;

/*
PROC PRINT DATA = DF1;
RUN;
*/

DATA C2;
  SET C2;
  TP='COVPARM';
RUN;
DATA F2;
  SET F2;
  TP='FIXED  ';
RUN;

DATA DF2;
  LENGTH P $24;
  LENGTH MODEL $12;
  SET F2(RENAM=(EFFECT=P) ) C2(RENAM=(COVPARM=P));
  IF ESTIMATE NE 0;
  DUM=1;
  MODEL='REDUCED';
  KEEP MODEL TP ESTIMATE STDERR P DUM;
RUN;

/*
PROC PRINT DATA = DF2;
RUN;
*/
```

```
DATA DF;
  SET DF1 DF2;
  RUN;

/*
PROC PRINT DATA = DF;
RUN;
*/

PROC SORT DATA = DF;BY MODEL;RUN;
PROC UNIVARIATE DATA = DF NOPRINT;
BY MODEL;
VAR DUM;
OUTPUT OUT=DF_ SUM=DF;
RUN;

/*
PROC PRINT DATA = DF_;
RUN;
*/

PROC TRANSPOSE DATA = DF_ OUT=DFT(DROP=_NAME_ _LABEL_);
VAR DF;
ID MODEL;
RUN;

DATA DFT;
  SET DFT;
  DUM=1;
RUN;

/*
PROC PRINT DATA = DFT;
RUN;
*/

DATA LOGL1;
  SET FIT1(RENAM=(VALUE=NEG2LOGLFULL));
  IF SUBSTR(DESCR,1,2)=' -2';
  DUM=1;
  KEEP DUM NEG2LOGLFULL;
RUN;

DATA LOGL2;
  SET FIT2(RENAM=(VALUE=NEG2LOGLRREDUCED));
  IF SUBSTR(DESCR,1,2)=' -2';
  DUM=1;
  KEEP DUM NEG2LOGLRREDUCED;
RUN;

PROC SORT DATA = DFT;BY DUM;RUN;
PROC SORT DATA = LOGL1;BY DUM;RUN;
PROC SORT DATA = LOGL2;BY DUM;RUN;

DATA LOGL;
  MERGE LOGL1 LOGL2 DFT;
  BY DUM;
  CHI=NEG2LOGLRREDUCED - NEG2LOGLFULL;
  DF=FULL-REDUCED;
  PDOSEREPONSE=PUT(1-CDF('CHISQUARE',CHI,DF),PVALUE6.4);
RUN;

PROC PRINT DATA = LOGL;
TITLE 'PRIMARY ANALYSIS DOSE RESPONSE UNION INTERSECTION P-VALUE';
RUN;
TITLE;
QUIT;
```

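### The Appendix D template counts degrees of freedom instead of using the stated 6, which can give 5 or 7, and its full-model contrasts against the reference arm are non-estimable as written

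*SAP*

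**What the plan says.** SAP 13.3.3 fits the random coefficients model with and without the treatment-by-time and treatment-by-time-squared interactions. "The difference in -2 log likelihood between models will be compared to the" chi-square distribution, with df given as 6. The null is rejected if it "can be rejected at the 10% alpha level". If the variance of time or of time squared is estimated as zero, the term is kept as a fixed effect and the analysis is re-run. The section points to Appendix D for example code because the programming is complex.

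Appendix D does not use the number 6. It stacks the fixed-effect solutions and the covariance parameters of each model, keeps the rows that pass "IF ESTIMATE NE 0", counts them, and sets "DF=FULL-REDUCED". The printed result is titled as the primary-analysis dose-response p-value.

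SAP 13.4.1 also refers to Appendix D for the first secondary analysis. That analysis needs each dose-placebo difference at 4, 8 and 12 weeks with confidence interval and p-value, and linear and quadratic contrasts at 12 weeks. In the full-model code, the group 1 minus group 3 difference ends with "TIME*TIME 0 G*TIME*TIME 360000 0 0".

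**The concern.** The non-zero filter removes the reference-level rows, which SAS prints as zero. It also removes any variance component estimated at zero. With three random components and three post-baseline visits, zero estimates are foreseeable, and the SAP provides for them. If a component is zero in one model but not in the other, the primary p-value comes from the wrong reference distribution for a reason unrelated to treatment.

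The method is reused on the 20 imputed data sets, in the per-protocol and mITT sets, in every subgroup, and for 17-OHP and ACTH, so the miscount has several chances to occur.

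The contrast problem is of another kind. It does not depend on the data: it occurs whenever the coefficient pattern is copied.

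**Working it through.** **Reproducing 6 df.** Inputs: the model in SAP 13.3.2, with four arms coded "1 = 200mg tildacerfont, 2 = 100mg tildacerfont, 3 = 50mg tildacerfont and 4 = placebo"; random intercept, time and time squared, plus residual.

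- Reduced model, fixed effects: intercept, log baseline A4, sex, GC dose, time, time squared and 3 treatment terms = 9. Covariance parameters: 4. Count = 9 + 4 = 13.
- Full model: 9 + 3 (treatment by time) + 3 (treatment by time squared) = 15 fixed. Count = 15 + 4 = 19.
- 19 - 13 = 6, as stated.

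**Counting rule with zero components.** df = 6 - (zeros in full model) + (zeros in reduced model).

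- Same number of zeros in both: 6.
- One zero in the full model only: 18 - 13 = 5.
- One zero in the reduced model only: 19 - 12 = 7.
- With up to three zeros per model, the possible range is 3 to 9.

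**Effect on p** (upper chi-square tail):

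| Statistic | 5 df | 6 df | 7 df |
|---|---|---|---|
| 9.5 | 0.091 | 0.147 | 0.219 |
| 11.0 | 0.051 | 0.088 | 0.139 |
| 12.0 | 0.035 | 0.062 | 0.101 |

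At 10%, 9.5 is wrongly significant on 5 df, and 11.0 is wrongly non-significant on 7 df. If the true reference is chi-square on 6 df, the 10% critical value for 5 df (9.236) has size 16.1% and that for 7 df (12.017) has size 6.2%. At 5% the sizes are 8.6% and 2.9%.

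**The appendix's own data.** Both models were refitted by maximum likelihood outside SAS. -2 log likelihood is 576.70 (reduced) and 538.95 (full), a difference of 37.75. The time-squared variance is zero in both models, so the count is 4, correct for three groups (2 x 2). A test run on the example would not reveal the fault.

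**How often.** The documents give no variance components, so these are assumptions.

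- 18 per arm; visits near days 28, 56 and 84; time in units of 84 days; 200 data sets per scenario; variances (intercept, time, time squared, residual) of (0.15, 0.10, 0.05, 0.10), (0.15, 0.10, 0, 0.10) and (0.20, 0, 0, 0.12). With no treatment effect, the count missed 6 in 8% to 10% of data sets. With the first set of variances and an assumed slope of -0.7 in every active arm, it missed in 24.5%. Every miss was 5 or 7. Rejection rates at 10% on 6 df versus the counted df were 14.0% and 14.0%, 11.5% and 11.0%, 13.0% and 12.0%, and with the slope 80.0% and 78.5%.
- Log SD 0.5, compound-symmetric or AR(1) errors, 15 or 18 per arm, 100 trials per scenario. Without the re-run rule, the count missed in 3% to 21%, and the 10% decision changed in 0% to 3%. With zero time or time-squared terms dropped from both models and re-run, it missed in 0%.

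SAS was not run, and these frequencies depend on the numerical tolerance for zero.

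**Estimability.** A data row from group g at time t puts t squared on `TIME*TIME` and the same value on that group's `G*TIME*TIME` column. In an estimable function the `G*TIME*TIME` coefficients must therefore sum to the `TIME*TIME` coefficient.

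| Full-model line (day 600) | TIME*TIME | G*TIME*TIME | Sum | Condition met |
|---|---|---|---|---|
| Group 1 value | 360000 | 360000, 0, 0 | 360000 | yes |
| Group 2 value | 360000 | 0, 360000, 0 | 360000 | yes |
| Group 3 value | 360000 | 0, 0, 0 | 0 | no |
| 1 minus 3 | 0 | 360000, 0, 0 | 360000 | no |
| 2 minus 3 | 0 | 0, 360000, 0 | 360000 | no |
| Linear | 0 | -360000, 0, 0 | -360000 | no |
| Quadratic | 0 | 360000, -720000, 0 | -360000 | no |

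Projecting each vector on the row space of the design matrix gives the same answers. With the reference coefficient added, 1 minus 3, linear, quadratic and the group 3 value become estimable; 2 minus 3 has the same form as 1 minus 3. The reduced-model contrasts contain no interaction terms, and those tested (1 minus 3, linear, quadratic) are estimable.

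**The case against.** The text of 13.3.3 fixes df at 6, and the code is labelled as an example. It analyses untransformed pulse in three groups, without sex or GC dose, and must be rewritten for this trial. One can also read the model fitted with and without the interactions as two fits that differ in nothing else, so that the re-run rule would apply to both. On that reading the miscount from the time terms disappears. The failed contrasts would be visible, because PROC MIXED reports a non-estimable function rather than a wrong number, and 13.4.1 defines the intended differences in words.

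Most of this stands, and it limits the point. What remains is that the df rule is generic and would carry over unchanged into the adapted program. The re-run rule is silent on matching random terms and on a zero intercept variance. The visible contrast failure would have to be repaired after the plan was final.

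A reader might infer that any boundary variance estimate would push the primary p-value across the threshold. The documents do not support that: a zero in both models leaves 6 df, and few statistics lie close enough to the critical value. Nor are all the template's contrasts broken; the fault lies in the full model only.

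**Conclusion.** Two template errors and one gap in wording; not a defect in the pre-specified primary test, whose df of 6 is correct. The df error is conditional and can go either way: 5 df is anti-conservative, 7 df conservative. It could change the decision in an individual trial, but under the assumed variances this was uncommon (0% to 3% without the re-run rule), and average rejection rates moved by at most 1.5 percentage points. The miscount largely disappears if the rule is applied to both models.

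The contrast error is certain if the pattern is copied. It affects five full-model lines and leaves the first secondary analysis without drug-placebo differences or dose contrasts until it is repaired.

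The 10% level in 13.3.3 also conflicts with Protocol 9.4.1 ("All efficacy analyses will be conducted on the ITT Population using a 2-sided alpha of 0.05"). That is a separate matter; the df point holds at either level.

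**What to change.** 1. In Appendix D, set df to 6, or count fixed effects only (15 - 9 = 6).
2. In 13.3.3, state that the full and reduced models must have identical random terms, and that any component estimated as zero in either model, the intercept included, is dropped from both before the re-run.
3. Complete the reference-arm `G*TIME*TIME` coefficient in every affected line: -360000 for the two drug-reference differences; +360000 for the linear contrast, the quadratic contrast and the reference-arm value. Correcting only the drug-reference lines would leave the dose contrasts required by 13.4.1 non-estimable.
4. Rewrite the lines for four arms with placebo last and for the trial's own days. At 12 weeks (day 84, 84 x 84 = 7056), 200 mg minus placebo takes 84, 0, 0, -84 on treatment by time and 7056, 0, 0, -7056 on treatment by time squared.

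The cost is a few lines of code and one sentence of text, with no change to design, data or sample size.

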## 21 Appendix E: Calculating Absolute CFB and Absolute Treatment Effects for A4 at Based on Analyses Conducted on the Log Scale.

The A4 Primary Efficacy Analysis is conducted on the log scale due to the inherent skewness and non-Normality of untransformed A4 values. While back transformation of log scale analysis results leads to interpretable quantities on the ratio scale, interest still resides in appreciation of the results on the absolute scale in ng/dL units. Given the non-Normality of A4 values, a simplistic analysis of  $CFB = (\text{Week 18 A4 value} - \text{baseline A4 value})$  is inappropriate as this simple CFB will also be non-Normal, resulting in upwardly biased estimates of mean A4 level and inflated SDs and SEs.

Thus, to address the Second Secondary Efficacy Analysis ([Table 1](#), Analysis 2.2), the Primary Analysis repeated measures random coefficients mixed-effects model will be re-run exactly as described in [Section 13.3.3](#) but with log A4 as the dependent variable as opposed to the change (i.e. as opposed to log A4 value minus log baseline value). Note, this re-run of the model with log A4 as the dependent variable will give precisely the same results, parameter estimates and variance-covariance matrix estimate as the analysis with log A4 minus log baseline as the dependent variable. The resulting estimates of mean log A4 and mean change from baseline in log A4 will be used via the Delta Theorem to provide consistent estimate of A4 treatment effects on the absolute scale.

### Delta Theorem

Suppose  $x_{ij}$  are independent, identically distributed Normal random variables with  $i = E$  and  $C$  representing experimental and control treatments, and  $j = 1 \dots n_i$  representing subject number. Then  $x_{ij} \sim N(\mu_i, \sigma^2)$  and  $\bar{x}_i \sim N(\mu_i, \sigma^2/n_i)$ .

Suppose there is interest in the function of  $\bar{x}_i$ , i.e.,  $u_i = f(\bar{x}_i)$ . Then, the delta theorem (= first order Taylors expansion of  $u_i$ ) as described by Armitage et al ([Armitage 2010](#)) states that the variance of  $u_i$  is given by

$$Var(u_i) = \left[ \frac{\partial f}{\partial \bar{x}_i} \right]^2 Var(\bar{x}_i)$$

And, further,

$$Var(u_E - u_C) = \left[ \frac{\partial f}{\partial \bar{x}_E} \right]^2 Var(\bar{x}_E) + \left[ \frac{\partial f}{\partial \bar{x}_C} \right]^2 Var(\bar{x}_C) + 2 \left[ \frac{\partial f}{\partial \bar{x}_E} \right] \left[ \frac{\partial f}{\partial \bar{x}_C} \right] Cov(\bar{x}_E, \bar{x}_C)$$

In the case of the Primary Efficacy Analysis, let  $\bar{x}_i$  represent the estimated A4 CFB on the log scale,  $L_i$ , with  $Var(L_i) = [SE(\bar{x}_i)]^2$  and  $Cov(L_E, L_C) = Cov(\bar{x}_E, \bar{x}_C)$  where  $Cov(\dots)$  denotes covariance.

Interest lies in A4 on the absolute scale, i.e. in the function  $f(y) = e^{-y}$ , and thus in the function  $u_i = e^{-L_i}$ . Hence,

$$Var(u_i) = [-e^{-L_i}]^2 Var(L_i) = e^{-2L_i} \cdot Var(L_i)$$

and

$$Var(u_E - u_C) = e^{-2L_E} \cdot Var(L_E) + e^{-2L_C} \cdot Var(L_C) + 2 Cov(L_E, L_C) \cdot e^{-L_E} \cdot e^{-L_C}$$

Hence, the estimate of the absolute difference in mean A4 values,  $E - C$ , is given by

$u_E - u_C = e^{-L_E} - e^{-L_C}$  with  $SE(u_E - u_C) = \sqrt{Var(u_E - u_C)}$  such that the  $100(1 - \alpha)\%$  CI is given by

$$(u_E - u_C) \pm t_{df, \alpha/2} \cdot \sqrt{Var(u_E - u_C)}$$

where  $t_{df, \alpha/2}$  represents the  $(1 - \alpha/2)$  percentile of the studentized  $t$  cumulative distribution function on  $df$ , where  $df$  is the error degrees of freedom associated with the corresponding log scale A4 treatment effect estimate at 18 Weeks from the Primary Efficacy Analysis model.

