#### **13.4.2 Second Secondary Efficacy Analysis**

The preceding estimated mean change from baseline in A4 is conducted on the log scale due to the inherent skewness and non-Normality of untransformed A4 values. While back transformation of log scale analysis results leads to interpretable quantities on the ratio scale, interest still resides in appreciation of the results on the absolute scale in ng/dL units.

Given the non-Normality of A4 values, a simplistic analysis of  $CFB = (\text{Week 18 A4 value} - \text{baseline A4 value})$  is inappropriate as this simple CFB will also be non-Normal, resulting in upwardly biased estimates of mean A4 level and inflated SDs and SEs; consequently power will also be eroded.

Thus, to address the Second Secondary Efficacy Analysis (see [Table 1](#), Analysis 2.2) and facilitate the presentation of results on both the ratio (i.e. % change) and absolute scales, the Primary Analysis repeated measures random coefficients mixed-effects model will be re-run exactly as described in [Section 13.3.3](#) but with log A4 as the dependent variable as opposed to the change (i.e. as opposed to log A4 value minus log baseline value). Note, this re-run of the model with log A4 as the dependent variable will give precisely the same results, parameter estimates and variance-covariance matrix estimate as the analysis with log A4 minus log baseline as the dependent variable.

As described with example SAS codes in Appendix E, the delta theorem will be applied to the log scale results to provide consistent estimates of the CFB in A4 values on the absolute scale

together with an estimate for the difference in LSmeans and the associated 95% CI. Results will be presented for the absolute change in A4 at 4, 8 and 12 weeks of double blind randomized treatment. A serial plot will be presented of the estimated absolute mean change from baseline in log A4 over time. The y-axis will be the CFB in ng/dL and the x-axis will display baseline, week 4, week 8 and week 12 of double blind randomized treatment. All treatment groups will be presented on the graph.

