## Example SAS Code

The following SAS codes provides an illustrative application of the Delta Theorem.

```
OPTIONS PAGESIZE=58 LINESIZE=180 NONUMBER NODATE;

** DEPENDENT VARIABLE IS LOG PULSE ** ;
PROC MIXED DATA=STUDY2 COVTEST NOCLPRINT METHOD=ML;
  CLASS ID G T;
  MODEL LPULSE = LBASE T G T*G / SOLUTION OUTP=PRED1R OUTPM = PRED1F;
  REPEATED T / TYPE=UN SUBJECT = ID;
  LSMEANS T*G / PDIFF DIFF ALPHA=0.05 CL COV;
  ODS OUTPUT LSMEANS=LSM;
  ODS OUTPUT DIFFS=LSMDIFF;
  TITLE 'LOG ABS MMRM';
  RUN;
  TITLE;

*** TRT EFFECT BASE ON ABSOLUTE SCALE **;
%MACRO ABSTRTEFF(DRUG,PCBO,T,CVPOS,DAT);
DATA DRUG;
  SET LSM;
  LENGTH LABEL $12.;
  LABEL=LEFT(TRIM(PUT(&DRUG,1.0)))||' V '||LEFT(TRIM(PUT(&PCBO,1.0)));
  IF T=&T AND G=&DRUG;
  CV=COV&CVPOS;
  TIME=&T;
  DRUG=ESTIMATE;
  SEDRUG=STDERR;
  DF=DF;
  KEEP LABEL TIME DF DRUG SEDRUG CV;
RUN;
DATA PCBO;
  SET LSM;
  LENGTH LABEL $12.;
  LABEL=LEFT(TRIM(PUT(&DRUG,1.0)))||' V '||LEFT(TRIM(PUT(&PCBO,1.0)));
  IF T=&T AND G=&PCBO;
  TIME=&T;
  PCBO=ESTIMATE;
  SEPCBO=STDERR;
  KEEP LABEL TIME PCBO SEPCBO;
RUN;
PROC SORT DATA = DRUG;BY LABEL TIME;RUN;
PROC SORT DATA = PCBO;BY LABEL TIME;RUN;
DATA COMB&DAT;
  MERGE DRUG PCBO;
  BY LABEL TIME;
  ABSDRUG=EXP(DRUG);
  ABSPCBO=EXP(PCBO);
  ABSEFF= ABSDRUG-ABSPCBO;
  ABSDRUGV= SEDRUG**2*ABSDRUG**2;
  ABSPCOV= SEPCBO**2*ABSPCBO**2;
  V = SEDRUG**2*ABSDRUG**2 + SEPCBO**2*ABSPCBO**2 - 2*CV*ABSDRUG*ABSPCBO;
  ABSLOWER = ABSDRUG-ABSPCBO - SQRT(V)*QUANTILE('T',0.975,DF);
  ABSUPPER = ABSDRUG-ABSPCBO + SQRT(V)*QUANTILE('T',0.975,DF);
  ABSP = 2*(1-CDF('T',ABS(ABSDRUG-ABSPCBO)/SQRT(V),DF));
RUN;
```

```
%MEND ABSTRTEFF;

%ABSTRTEFF(1,3,1,7,1);
%ABSTRTEFF(1,3,2,7,2);
%ABSTRTEFF(1,3,3,7,3);
%ABSTRTEFF(2,3,1,7,4);
%ABSTRTEFF(2,3,2,7,5);
%ABSTRTEFF(2,3,3,7,6);

DATA COMB;
  SET COMB1 COMB2 COMB3 COMB4 COMB5 COMB6;
RUN;

PROC PRINT DATA = COMB;
  TITLE 'TREATMENT EFFECT ON ABSOLUTE SCALE';
RUN;
TITLE;

** DEPENDENT VARIABLE IS NOW LOG CHANGE = LOG PULSE - LOG BASE ** ;
PROC MIXED DATA=STUDY2 COVTEST NOCLPRINT METHOD=ML;
  CLASS ID G T;
  MODEL LCFB = LBASE T G T*G / SOLUTION OUTP=PRED1R OUTPM = PRED1F;
  REPEATED T / TYPE=UN SUBJECT = ID;
  LSMEANS T*G / PDIFF DIFF ALPHA=0.05 CL COV;
  ODS OUTPUT LSMEANS=LSM_;
  ODS OUTPUT DIFFS=LSMDIFF_;
  TITLE 'LOG CFB MMRM';
RUN;
TITLE;

DATA LSMDIFF_;
  SET LSMDIFF_;
  IF T = _T AND G NE _G ;
  IF _G=3;
  TIME=T;
  LABEL=LEFT(TRIM(PUT(G,1.0)))||' V '||LEFT(TRIM(PUT(_G,1.0)));
  KEEP ESTIMATE STDERR LOWER UPPER PROBT TIME LABEL;
RUN;

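### The delta-method formulas in SAP Appendix E use exp(-L) and +2Cov; followed as written they reverse the sign of the absolute A4 effect, are not in ng/dL and give a wrong variance, and the example code beside them contradicts them.

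*SAP*

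**What the plan says.** SAP Section 13.4.2 (secondary analysis 2.2) re-runs the random-coefficients model of Section 13.3.3 with log A4 as the dependent variable. It then applies the delta theorem of Appendix E "to provide consistent estimates of the CFB in A4 values on the absolute scale". The introduction to Appendix E gives the purpose: "interest still resides in appreciation of the results on the absolute scale in ng/dL units".

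The Delta Theorem subsection lets the generic mean "represent the estimated A4 CFB on the log scale", calls it L, and continues "Interest lies in A4 on the absolute scale, i.e. in the function" f(y) = exp(-y). The negative exponent then appears in the derivative, in Var(u), in Var(u_E - u_C) and in the estimator exp(-L_E) - exp(-L_C), which is described as "the estimate of the absolute difference in mean A4 values". Both the general and the A4-specific expression for Var(u_E - u_C) add twice the covariance term.

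The example code that follows is described as illustrative. It models the log of the post-baseline value, back-transforms with EXP(DRUG) and EXP(PCBO), takes their difference, and subtracts 2*CV*ABSDRUG*ABSPCBO in the variance.

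Section 13.4.5 applies the same method to 17-OHP (analysis 2.5), and Section 13.5.8 extends the secondary methods to ACTH, including its absolute change (analysis 3.13).

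**The concern.** The written formula and the code are two different estimators, and the SAP does not say which prevails. The formula is the formal specification and the code is only an illustration, so a programmer or a validating statistician could reasonably implement the formula. Two listed secondary analyses and one exploratory analysis would then show a beneficial reduction as a positive number with no physical unit.

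The code cannot simply replace the text either. It fits a categorical-visit MMRM to three-group pulse data, whereas Section 13.4.2 asks for the continuous-time random-coefficients model. It also prints no within-arm absolute change from baseline, although that is how endpoint 2.2 is worded.

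**Working it through.** The plan states no numerical result here, so the check is of algebra, illustrated with assumed A4 values and with the example data in SAP Appendix D.

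**1. Sign.** exp(-L) decreases in L. If L_E < L_C (drug lowers A4 more), exp(-L_E) - exp(-L_C) is always positive. Assume a baseline of 500 ng/dL; the documents give no A4 means by arm.

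| Drug ratio / placebo ratio to baseline | Intended effect | Text, L = log change | Text, L = log A4 |
|---|---|---|---|
| 0.5 / 1.0 | 250 - 500 = -250 ng/dL | 1/0.5 - 1/1.0 = +1.0 | 1/250 - 1/500 = +0.0020 |
| 0.7 / 0.95 | 350 - 475 = -125 ng/dL | 1/0.7 - 1/0.95 = +0.376 | 1/350 - 1/475 = +0.00075 |

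**2. Units.** With L as the log change, exp(-L) is baseline divided by post-baseline. It has no unit, and the +1.0 is the same at a baseline of 500 or 1000. With L as log A4, exp(-L) is 1/A4, in dL/ng. Neither is ng/dL. Changing only the exponent is not enough, because exp(+log change) is still a ratio; L must be mean log A4.

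**3. Variance.** For u = exp(L), the first-order result is

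Var(u_E - u_C) = exp(2L_E)Var(L_E) + exp(2L_C)Var(L_C) - 2exp(L_E + L_C)Cov(L_E, L_C).

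A simulation of 2,000,000 draws (means 250 and 500, log SE 0.2, correlation set to 0.3 to make the sign visible) gave an SD of 100.6 for the difference. The formula gives 97.5 with -2Cov and 124.5 with +2Cov, so the minus sign is right.

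**4. The SAP's own example.** The Appendix E model (ML, unstructured covariance, log baseline as covariate) was refitted to the Appendix D data. At the third time point the back-transformed means are 93.9 (group 1) and 128.9 (group 3), with geometric-mean baseline 93.1.

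- Code formula, group 1 v 3: 93.9 - 128.9 = -35.0 bpm, SE 3.40.
- Text formula, L = log change: 93.1/93.9 - 93.1/128.9 = 0.991 - 0.722 = +0.269, SE 0.0246.
- Text formula, L = log value: +0.00289, SE 0.000265.
- Group 2 v 3: code -30.3 bpm (SE 3.33); text +0.222 or +0.00238.

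**5. Size of the covariance part.** With equal weights, the ratio of the SE using +2Cov to the SE using -2Cov is sqrt((1 + r)/(1 - r)), where r is the correlation between the two arms' estimates. In the example r runs from -0.005 to -0.07 across comparisons and time points. At r = -0.06 the ratio is sqrt(0.94/1.06) = 0.94, so the text SE is about 6% too small. For group 2 v 3 (r = -0.005) the difference is about 0.5%.

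**The case against.** The best defence is that a competent programmer would not be misled. Section 13.4.2 already asks for log A4 as the dependent variable, Section 13.4.1 back-transforms with the correct sign, and the example code has the right exponent and covariance sign. A result of +1.0 ng/dL would visibly contradict analysis 2.1. SAP Section 10.5 gives the secondary endpoints no alpha control, and the p-value the example code prints is the log-scale one. All of that stands, and it limits the likely damage. It does not make the written rule correct or say that the code overrides it.

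Three stronger readings are tempting and are not supported.

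- **Wrong covariance index.** A reader might infer that passing covariance column 7 for all three time points gives wrong standard errors at the second and third. In the coded model, group-by-visit is saturated and the baseline slope is common, so between-arm covariance comes only from that slope. With complete data, as in Appendix D, it does not depend on the visit. In the refit, the covariance between groups 1 and 3 is -0.0000257 for every pairing of visits. Re-indexing a three-group example for four arms is routine adaptation.
- **Inflated standard errors.** A reader might assume that +2Cov inflates the SE substantially. That needs a sizeable positive between-arm correlation. This correlation comes only from shared covariates, and in the SAP's example it is small and negative, so the SE shrinks slightly.
- **Bias from geometric means.** Section 13.4.2 deliberately avoids arithmetic means because A4 is skewed. Back-transforming a mean log gives a geometric mean, so the complaint concerns the label, not the choice.

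**Conclusion.** The Delta Theorem text is wrong in three ways and contradicts the code beside it. The sign reversal and the loss of units follow from the algebra and need no assumed values. The magnitudes shown for A4 rest on assumed baselines and ratios. The covariance-sign error is real but minor, a few percent of the SE in either direction.

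The repetition of the negative exponent through function, variance and estimator makes a PDF-reading artefact implausible. The reach is secondary analyses 2.2 and 2.5 and exploratory analysis 3.13. The primary dose-response test and the ratio-scale results do not use this formula. A reader might infer that the trial will report the wrong sign; the documents show only that the written rule would produce it and that the example code would not. The point should be corrected before programming, but it does not threaten the primary conclusion.

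**What to change.** In the Delta Theorem subsection of Appendix E:

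1. Define L as the model-estimated mean log A4 at the stated time point, from the random-coefficients model of Section 13.3.3 re-run with log A4 as the dependent variable.
2. Set u = exp(L), with Var(u) = exp(2L)Var(L).
3. Use the variance of the difference in step 3 of the working, with -2Cov in both the general and the A4-specific formula. Take Cov from that model's drug and placebo estimates at the same time point.
4. Define within-arm absolute change as exp(L) minus the back-transformed baseline at which L is evaluated, and add it to the output.
5. Label the results as geometric means and differences in geometric means (ng/dL), here and where Section 13.4.2 claims a consistent estimate of the absolute change.
6. Carry the same wording to 17-OHP and ACTH, and state that the corrected formulas govern if the example code differs.

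The cost is a short SAP text change and a few lines of code. No data collection, sample size or primary analysis is affected.
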